### 7.3. Exploratory Endpoints and Analyses

Efficacy will be evaluated for the Phase 1b MAD portion of the study as an exploratory endpoints and details are noted throughout sections 7.1 and 7.2. Exploratory endpoints and analyses may be included in relation to the Phase 2 POC part of the study as described within this section.

#### 7.3.1. CCI

CCI

Sponsor: Boston Pharmaceuticals, Inc.  
Protocol Number: BOS161721-02  
SAP Version and Date: Version 3.0, 13Nov2020

CCI

CCI

CCI

## 8. PHARMACOKINETICS/PHARMACODYNAMICS/IMMUNOGENICITY

Pharmacokinetics, pharmacodynamics, and immunogenicity are secondary endpoints for the Phase 1b MAD study and exploratory endpoints for the Phase 2 POC study.

PD results reported as less than the lower limit of quantification (LLOQ) will be counted as 0 to calculate summary linear statistics and will be reported as <LLOQ in listings. All observed Immunogenicity and PD data, as provided by an external vendor, will be presented in by-patient listings.

SAPs describing analyses (pharmacokinetics [PK], PK/pharmacodynamics[PD], etc.) not covered within this SAP will be included within an Appendix of this document. The author, finalization date, signatories, and page numbering of this SAP are independent of those SAPs and vice versa. Only the last final versions will be included in the appendix just prior to study conclusion.

### 8.1. Pharmacokinetics

BOS161721 PK concentration and parameter analyses will performed by a separate PK vendor and described under a separate SAP.

## 8.2. Pharmacodynamics

Descriptive statistics for the observed results of the following PD endpoints/results will be summarized separately at baseline and each visit. Change from baseline and percentage change from baseline will be summarized at each post-baseline visit. In cases where both numeric and qualitative results are provided, the summaries will be based on the numeric results. In cases where only qualitative results are provided and results given only as titers, shifts will be summarized. Graphical presentations of mean and SD of the change from baseline over time will also be presented for the parameters in table 6.

**Table 6**

| PD Endpoint   | Applicable Study Portion(s) | Parameters to be Included in Summary Tables and Figures ('NA (all)' is displayed if all collected parameters are to be included) |
|--|------------------------------------|---|
| Clinical PD Biomarkers  |                                    |   |
| CCI [REDACTED]   | MAD and POC                        | NA (all)  |
| C-Reactive Protein   | MAD and POC                        | NA (all)  |
| CCI [REDACTED]   | MAD and POC                        | NA (all)  |
| CCI [REDACTED]   | MAD and POC                        | NA (all)  |
| CCI [REDACTED]   | MAD and POC                        | NA (all)  |
| CCI [REDACTED]   | MAD and POC                        | NA (all)  |
| CCI [REDACTED]   | MAD and POC                        | NA (all)  |
| Other Biomarkers  |                                    |   |
| Phosphorylated signal transducer and activator of transcription 3 (pSTAT3) | MAD only                           | % pSTAT3+ Lymphocytes –Stimulated; Ratio MEF (Stimulated / Unstimulated)  |

| PD Endpoint                                | Applicable Study Portion(s) | Parameters to be Included in Summary Tables and Figures ('NA (all)' is displayed if all collected parameters are to be included)   |
|--|-----------------------------|--|
| Leukocyte immunophenotype (B and NK Cells) | MAD only                    | CD19+% of CD45+ Lymphocytes;
IgD+C27-% of CD19+;
IgD+CD27-CD38++CD24++% of CD19+;
IgD-CD27-% of CD19+;
IgD+CD27+% of CD19+;
IgD-CD27+% of CD19+;
IgD-CD27+CD38++CD138-% of CD19+;
IgD-CD27+CD38++CD138+% of CD19+;
CD56+% OF CD45+ Lymphocytes |
| Leukocyte immunophenotype (T-Cells)        | MAD only                    | CD4+CD8-% of CD3+;
CXCR5+% of CD4+CD8-;
PD-1+% of CD4+CD8-;
ICOS+% of CD4+CD8-;
CD25+CD127-% of CD4+CD8-;
CXCR5+% of CD25+CD127-;
PD-1+% of CD25+CD127-;
ICOS+% of CD25+CD127-;
CD8+CD4-% of CD3+  |
| CCI [REDACTED]                             | MAD only                    | CCI [REDACTED]
[REDACTED]
[REDACTED]
[REDACTED]   |
| CCI [REDACTED]                             | MAD and POC                 | CCI [REDACTED]
[REDACTED]   |
| CCI [REDACTED]                             | MAD and POC                 | Analyses planned for available CCI [REDACTED] data will be described in a separate SAP to be included in the appendix of this SAP.   |

CCI

CCI

Additional PD results may be plotted over time by treatment group and visit.

### 8.3. Immunogenicity

Immunogenicity data as collected on the eCRF will be provided in by-patient data listings including neutralizing antibodies (NAb) and ADA for all relevant timepoints.

All serum ADA samples that are confirmed positive in the ADA assay will be analyzed for the presence of NAb.

The proportion of patients with positive or negative ADA will be summarized by study phase, treatment group, and overall, at baseline (pre-dose), and post-baseline in the FAS. The frequency and percentage of patients with transient positive and persistent positive ADA will also be included in the summary. If warranted based on data, treatment-emergent transient positive and treatment-emergent persistent positive ADA will be summarized. The frequency and percentage of patients with confirmed positive, treatment-emergent confirmed positive, and negative ADA at each post-baseline timepoint will also be summarized. ADA designations and denominators are defined in table 7.

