|                                 | Negative           | Negative ADA at the post-baseline timepoint   |   |
| Overall                         | Positive           | A patient with positive baseline (pre-dose) ADA or positive post-baseline ADA   | Number of patients with a baseline or post-baseline ADA assessment                    |
|                                 | Negative           | A patient with negative baseline (pre-dose) ADA and negative post-baseline ADA at all time points   |   |

Sponsor: Boston Pharmaceuticals, Inc.  
Protocol Number: BOS161721-02  
SAP Version and Date: Version 3.0, 13Nov2020

[figure not shown]
The frequency and percentages of positive and negative neutralizing antibodies will be summarized in the FAS overall and at each relevant post-baseline timepoint (i.e., Day 15, Day 30, Day 60, Day 90, Day 180, Day 270). The denominators will be the number of patients with non-missing NAb data overall and at each timepoint, respectively.

The adverse event overview table from section 10.1 will be repeated by post-baseline positive and negative ADA as defined in table 7 in the safety analysis set. Additional adverse event analyses may be performed by post-baseline transient positive and persistent positive.

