## 2. STUDY OBJECTIVES AND ENDPOINTS

### 2.1. Multiple Ascending Dose (MAD) Phase 1b Study

| Objectives   | Endpoints   |
|--|---|
| 
Primary
 

• To assess safety, tolerability, and immunogenicity of repeat doses of BOS161721 (20, 60, and 120 mg) administered subcutaneously (SC) in adult patients with moderately to severely active SLE on limited background standard of care treatment, in order to estimate the optimal dose.

 | 
Safety Endpoints
 

• Incidence and severity of adverse events (AEs) and serious adverse events (SAEs), related AEs, AEs leading to study drug discontinuation, AEs by severity and relatedness

• Injection site reactions

• Columbia Suicide Severity Rating Scale (C-SSRS)

• 12-lead electrocardiograms (ECGs) parameter results at each visit and change from baseline

• Vital signs (blood pressure [BP], heart rate, and temperature) parameter results at each visit and change from baseline

• Clinical laboratory results and change from baseline

• Physical examinations changes from baseline

• Anti-drug antibodies (ADAs)

• Study drug exposure/compliance

 |

|   |   |
|---|---|

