# 6. STUDY PATIENT DATA

## 6.1. Analysis Populations/Sets

Full Analysis Set (FAS): Defined as all patients who receive at least one dose of study treatment and have at least one evaluable post-baseline efficacy evaluation (BILAG, PGA, SLEDAI-2K, CLASI, ACR-28, SLICC/ACR, CCI, or CCI). FAS analyses will be conducted on the basis of the randomized treatment. The FAS will be used as the basis for the primary efficacy analysis.

Safety Analysis Set (SS): Defined as all patients who receive at least one dose of study treatment. Safety analyses will be conducted on the basis of actual treatment received. The SS will be the basis of all safety reporting.

Per Protocol Set (PP): Defined to exclude major protocol violations from the efficacy analysis. The PP will include all patients from the FAS except those with major violations to the protocol deemed to impact the analysis of the primary endpoint. These violations will be identified based on blinded data prior to study unblinding. PP analyses will be conducted on the basis of the randomized treatment. Additional information on inclusion into this population can be found in Section 6.3.

Pharmacokinetic Analysis Set (PK): Defined as the FAS patients who received at least one dose of BOS161721 with sufficient concentration data for the calculation of at least one PK parameter.

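### ADA and NAb incidence is tabulated in the FAS but adverse events by ADA status in the safety set, so the two tables of SAP v3.0 Section 8.3 may count different patients

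*SAP*

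**What the plan says.** SAP v3.0 Section 8.3 sets three displays.

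- ADA status is "summarized by study phase, treatment group, and overall, at baseline (pre-dose), and post-baseline in the FAS".
- NAb frequencies are "summarized in the FAS overall and at each relevant post-baseline timepoint (i.e., Day 15, Day 30", with the list running on to Day 270.
- The adverse event overview of Section 10.1 is "repeated by post-baseline positive and negative ADA as defined in table 7 in the safety analysis set".

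Table 7 sets its denominators by available ADA assessments only. The NAb denominators are patients with non-missing NAb data.

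The analysis-set section of v3.0 is not in the pages available. Versions 1.0 and 2.0, bound into the same document, define the sets identically in Section 6.1. FAS patients must have received a dose and "have at least one evaluable post-baseline efficacy evaluation", chosen from a list of efficacy instruments. ADA is not among the instruments shown, two of which are redacted. "FAS analyses will be conducted on the basis of the randomized treatment". The other set reads: "Safety Analysis Set (SS): Defined as all patients who receive at least one dose of study treatment". For it, "Safety analyses will be conducted on the basis of actual treatment received".

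**The concern.** An antibody response to the drug follows from exposure. Whether a patient has an evaluable lupus assessment has no bearing on whether an ADA result is valid, yet the FAS would make that assessment a condition for being counted. The patients at risk of being left out are those who stop early. The treatment basis matters too, because an ADA response reflects the drug received, not the drug assigned.

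Section 8.3 already uses the safety set for the same Table 7 status in its adverse-event table. A reader who moves from the incidence table to that table may therefore meet two different counts of ADA-positive patients in one arm. The pages available give no reason for the split and plan no safety-set version of the incidence table.

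**Working it through.** **1. The two sets side by side** (SAP v1.0/v2.0 Section 6.1, assumed to carry into v3.0)

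| | FAS | Safety analysis set |
|---|---|---|
| Dose needed | at least one | at least one |
| Efficacy data needed | at least one evaluable post-baseline evaluation | none |
| Arm | as randomised | as treated |
| Use in v3.0 Section 8.3 | ADA and NAb incidence | AE overview by ADA status |

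Table 7's denominators apply within whichever set is named. They cannot bring back a patient who is outside the FAS.

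**2. A patient who leaves early.** Section 8.3 lists Day 15 as a NAb timepoint and sends confirmed-positive ADA samples for NAb testing, so an ADA sample exists at Day 15. In v2.0 Section 7.1.1, a BILAG, SLEDAI-2K or PGA result 0 to 25 days after the previous one is not evaluable. A dosed patient who gives the Day 15 sample and leaves without any evaluable efficacy assessment is in the safety set but not in the FAS.

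**3. A mis-dosed patient.** A patient randomised to placebo, given active drug in error and found ADA positive, counts under placebo in the incidence table. In the safety set the same patient counts under active.

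**4. Ceiling on the number affected.** The plan's own figures (v2.0 Section 3.3) reconcile: 132 / (1 − 24/156) = 156. Outside the FAS: 24/156 = 15.4%. At 2:1, 104 active and 52 placebo are randomised and 88 and 44 are in the FAS, leaving 16 active and 8 placebo outside. The share of these who were dosed and sampled is not stated, so the range is 0 to 24.

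**5. Illustration, Phase 2 active arm.** Assume 9/88 = 10.2% ADA positive in the FAS, with all 88 sampled. Add *k* dosed and sampled patients from outside the FAS. Incidence then lies between 9/(88 + *k*), if none is positive, and (9 + *k*)/(88 + *k*), if all are.

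| *k* | None positive | All positive |
|---|---|---|
| 4 | 9/92 = 9.8% | 13/92 = 14.1% |
| 8 | 9/96 = 9.4% | 17/96 = 17.7% |
| 16 (ceiling) | 9/104 = 8.7% | 25/104 = 24.0% |

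The error can go either way: leaving out ADA-negative early leavers overstates incidence.

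**6. Illustration, MAD cohort with 9 active patients.** Losing one ADA-positive patient changes 2/9 = 22.2% to 1/8 = 12.5%, or 1/9 = 11.1% to 0/8 = 0%. The positive counts in steps 5 and 6 are assumed, not taken from the plan.

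**The case against.** The strongest objection is that the governing definition is not visible. Version 3.0 did revise at least one analysis set (its Section 11 adds a criterion to the per-protocol set), so the FAS could have changed as well. This stands, and the point is conditional on it.

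The gap may also be empty. Any one of several instruments admits a patient to the older FAS. Appendix 13.1 of v3.0 refers to premature-discontinuation assessments in the protocol. If those apply to early leavers generally and include a qualifying instrument, such patients enter the FAS. That too stands: the gap is possible but not established. By-patient listings keep the results visible, although they do not correct the rates.

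A reader might infer more than the documents support:

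- *That v3.0 breaks its own rule that safety reporting uses the safety set.* The listing of ADA as a safety endpoint comes from superseded v1.0 and v2.0. Version 3.0 Section 8 classes immunogenicity as secondary in the MAD and exploratory in the POC, outside Section 10.
- *That the link from ADA to adverse events is estimated on mismatched populations.* The table that shows that link lies wholly in the safety set.
- *That the MAD dose choice was affected.* The role of immunogenicity in dose selection is stated in v1.0 and v2.0. Those versions referred ADA from their safety section to Section 8, which gave no FAS instruction. Nothing shown indicates that a FAS table informed the decision.
- *That early leavers with hypersensitivity or injection reactions are selectively removed.* This is plausible, but nothing in the plan shows it.

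**Conclusion.** The inconsistency within v3.0 Section 8.3 is real: the same ADA status is counted in the FAS for incidence and in the safety set for adverse events. If v3.0 keeps the earlier FAS definition, the incidence tables can leave out a dosed, sampled patient and can show a mis-dosed patient under the wrong treatment. The tables may disagree; it does not follow that they will. They differ only if at least one such patient exists.

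The size is unknown and may be zero. The 15.4% is no estimate of the loss, because patients never dosed are also outside the safety set and have no post-dose ADA result. The tables concerned are descriptive. The primary efficacy analysis and the AE-by-ADA table are not touched. This is a modest, avoidable defect, and it matters most where arms are small.

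**What to change.** First confirm the FAS definition in v3.0 Section 6.1. Then, in both places in Section 8.3 (the ADA summary and the NAb summary), replace the reference to the FAS with the Safety Analysis Set, by actual treatment received. Keep Table 7's ADA-assessment denominators and the stated NAb denominators. The incidence tables and the AE-by-ADA table will then draw on the same patients under the same treatment labels.

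The cost is one phrase in two places and a population flag in the ADA and NAb programs. No new data are needed.

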**Table 7**

| Timepoint                 | ADA Designations                 | Definition  | Denominator/Evaluable Patients   |
|---------------------------|----------------------------------|---|--|
| Baseline (Day 0 Pre-Dose) | Positive                         | Confirmed positive ADA at baseline                | Number of patients with a baseline and at least one post-baseline ADA assessment |
|                           | Negative                         | Negative ADA at baseline                          |  |
| Post-Baseline             | Positive                         | Confirmed positive ADA at any time after baseline | Number of patients with at least one post-baseline ADA assessment                |
|                           | Negative                         | Negative ADA at all times after baseline          |  |
|                           | Transient Positive iv | (1) Last ADA sampling timepoint is negative       |  |

Sponsor: Boston Pharmaceuticals, Inc.

Protocol Number: BOS161721-02

SAP Version and Date: Version 3.0, 13Nov2020

|                    |                                   |  |   |
|--------------------|-----------------------------------|--|---|
|                    |                                   | 
AND 2a OR 2b:
 
(2a) Only one post-baseline confirmed positive ADA (excluding the last sampling timepoint) exists
 
OR
 
(2b) Two or more post-baseline confirmed positive ADA where the first and last ADA confirmed positive samples are less than 16 weeks apart (irrespective of any negative ADA in between)
  |   |
|                    | Persistent Positive iv | 
1 OR 2 OR 3:
 
(1) Two or more post-baseline confirmed positive ADA where the first and last ADA confirmed positive samples are more than 16 weeks apart (irrespective of any negative ADA in between)
 
OR
 
(2) Confirmed positive ADA at the last post-baseline assessment
 
OR
 
(3) Negative ADA at the last post-baseline assessment and a prior confirmed positive ADA sample occurred less than 16 weeks before the last post-baseline negative ADA sample
 |   |
| Treatment-Emergent | Positive                          | 
A post-baseline confirmed positive result exists with a titer <math>\geq 4</math> times greater than the baseline titer
 
OR
   | Number of patients with at least one post-baseline ADA assessment |

Sponsor: Boston Pharmaceuticals, Inc.

Protocol Number: BOS161721-02

SAP Version and Date: Version 3.0, 13Nov2020

|  |                                  |  |  |
|--|----------------------------------|--|--|
|  |                                  | 
Any post-baseline confirmed positive result after a negative baseline result
 
Note: The number of treatment-emergent transient positive and treatment-emergent persistent positive ADA will sum to the total positive treatment-emergent ADA
 
Note: If baseline ADA data is missing, the baseline value is treated as negative for this analyses
  |  |
|  | Transient Positive iv | 
Scenario 1:
 
(1) Negative ADA at baseline
 
AND
 
(2) Last ADA sampling timepoint is negative
 
AND (3a OR 3b):
 
(3a) Only one post-baseline confirmed positive ADA (excluding the last sampling timepoint) exists
 
OR
 
(3b) Two or more post-baseline confirmed positive ADA where the first and last ADA confirmed positive samples are less than 16 weeks apart (irrespective of any negative ADA in between)
 
Scenario 2:
 
(1) Confirmed positive ADA at baseline
 
AND
 |  |

Sponsor: Boston Pharmaceuticals, Inc.

Protocol Number: BOS161721-02

SAP Version and Date: Version 3.0, 13Nov2020

|  |                                   |  |  |
|--|-----------------------------------|--|--|
|  |                                   | 
(2) Last ADA sampling timepoint is negative or is the same as baseline ADA levels
 
AND (3a OR 3b):
 
(3a) Only one post-baseline confirmed positive ADA (excluding the last sampling timepoint) exists and the titer at the post-baseline timepoint is <math>\geq 4</math> times greater than the baseline titer
 
OR
 
(3b) Two or more post-baseline confirmed positive ADA where the first and last ADA confirmed positive samples are less than 16 weeks apart (irrespective of any negative ADA in between) and the titers at each of the two or more post-baseline confirmed positive timepoints are <math>\geq 4</math> times greater than the baseline titer
 
Note: If baseline ADA data is missing, the baseline value is treated as negative for this analyses
 |  |
|  | Persistent Positive iv | 
Scenario 1:
 
(1) Negative ADA at baseline
 
AND (2 OR 3 OR 4):
 
(2) Two or more post-baseline confirmed positive ADA where the first and last ADA confirmed positive samples are more than 16 weeks apart (irrespective of any negative ADA in between)
 
OR
   |  |

Sponsor: Boston Pharmaceuticals, Inc.

Protocol Number: BOS161721-02

SAP Version and Date: Version 3.0, 13Nov2020

|  |  |   |  |
|--|--|---|--|
|  |  | 
(3) Confirmed positive ADA at the last post-baseline assessment
 
OR
 
(4) Negative ADA at the last post-baseline assessment and a prior confirmed positive ADA sample occurred less than 16 weeks before the last post-baseline negative ADA sample
 
Scenario 2:
 
(1) Confirmed positive ADA at baseline
 
AND (2 OR 3 OR 4):
 
(2) Two or more post-baseline confirmed positive ADA where the first and last ADA confirmed positive samples are more than 16 weeks apart (irrespective of any negative ADA in between) and the titers at each of the two or more post-baseline confirmed positive timepoints are <math>\geq 4</math> times greater than the baseline titer
 
OR
 
(3) Confirmed positive ADA at the last post-baseline assessment and the titer at the last post-baseline timepoint is <math>\geq 4</math> times greater than the baseline titer
 
OR
 
(4) Negative/similar to baseline ADA at the last post-baseline assessment and a prior confirmed positive ADA sample occurred less than 16 weeks before the last post-
 |  |
|--|--|---|--|

Sponsor: Boston Pharmaceuticals, Inc.

Protocol Number: BOS161721-02

SAP Version and Date: Version 3.0, 13Nov2020

|                                 |                    |   |   |
|---------------------------------|--------------------|---|---|
|                                 |                    | 
baseline negative/similar to baseline ADA sample and the titer of the confirmed positive ADA is <math>\geq 4</math> times greater than the baseline titer
 
Note: If baseline ADA data is missing, the baseline value is treated as negative for this analyses
  |   |
| Post-baseline at each timepoint | Positive           | Confirmed Positive ADA at the post-baseline timepoint   | Number of patients with ADA assessment at baseline and at the post-baseline timepoint |
|                                 | Treatment-Emergent | 
Scenario 1:
 
(1) Negative ADA at baseline
(2) Confirmed positive ADA at the post-baseline timepoint
 
Scenario 2:
 
(1) Confirmed positive ADA at baseline
(2) Confirmed positive ADA at the post-baseline timepoint and the titer at the of the confirmed positive ADA is <math>\geq 4</math> times greater than the baseline titer
 |   |
|                                 | Negative           | Negative ADA at the post-baseline timepoint   |   |
| Overall                         | Positive           | A patient with positive baseline (pre-dose) ADA or positive post-baseline ADA   | Number of patients with a baseline or post-baseline ADA assessment                    |
|                                 | Negative           | A patient with negative baseline (pre-dose) ADA and negative post-baseline ADA at all time points   |   |

Sponsor: Boston Pharmaceuticals, Inc.  
Protocol Number: BOS161721-02  
SAP Version and Date: Version 3.0, 13Nov2020

[figure not shown]
The frequency and percentages of positive and negative neutralizing antibodies will be summarized in the FAS overall and at each relevant post-baseline timepoint (i.e., Day 15, Day 30, Day 60, Day 90, Day 180, Day 270). The denominators will be the number of patients with non-missing NAb data overall and at each timepoint, respectively.

The adverse event overview table from section 10.1 will be repeated by post-baseline positive and negative ADA as defined in table 7 in the safety analysis set. Additional adverse event analyses may be performed by post-baseline transient positive and persistent positive.

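### SAP v3.0 Table 7: the transient and persistent ADA classes overlap, and some treatment-emergent positive patients fit neither, so the stated sum to the total does not hold

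*SAP*

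**What the plan says.** All references are to SAP v3.0, Section 8.3 and Table 7.

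- **Transient, last sample:** "Last ADA sampling timepoint is negative". Nothing is said about how long before it the last positive fell.
- **Transient, one positive (2a; 3a in the treatment-emergent rows):** "Only one post-baseline confirmed positive ADA (excluding the last sampling timepoint) exists".
- **Transient, several positives (2b; 3b):** "first and last ADA confirmed positive samples are less than 16 weeks apart".
- **Persistent, by span (1; treatment-emergent 2):** "first and last ADA confirmed positive samples are more than 16 weeks apart".
- **Persistent, by last sample (2; treatment-emergent 3):** the last post-baseline sample is positive.
- **Persistent, by recency (3; treatment-emergent 4):** "Negative ADA at the last post-baseline assessment and a prior confirmed positive ADA sample occurred less than 16 weeks before" the last negative sample.
- **Treatment-emergent, baseline-positive patients:** one post-baseline positive with a titre at least 4 times baseline is enough to be treatment-emergent positive. The two span rules (transient 3b, persistent 2) add that "the titers at each of the two or more post-baseline confirmed positive timepoints are" at least 4 times baseline.
- **Reconciliation note:** "The number of treatment-emergent transient positive and treatment-emergent persistent positive ADA will sum to the total positive treatment-emergent ADA".

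The post-baseline transient and persistent counts are committed outputs. The treatment-emergent split is produced only if the data warrant it, and the adverse event breakdown by these classes is optional. The text after the table lists timepoints for neutralizing antibodies: "i.e., Day 15, Day 30, Day 60, Day 90, Day 180, Day 270".

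**The concern.** The two classes are presented as a split of the positive patients, and for the treatment-emergent rows the table says so outright. The rules do not deliver a split. The recency rule for persistent ADA takes in patients who also satisfy the transient rule, because transient asks only that the last sample be negative, however recent the last positive. Separately, in baseline-positive patients the condition that makes someone treatment-emergent positive (one titre of at least 4 times baseline) is weaker than the condition in the span rules (every positive at that level), which opens a gap.

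A programmer following the text will produce rows that do not reconcile to the total, or will have to invent a precedence rule. If that happens after unblinding, how the positives divide between the two classes becomes a post hoc choice. Any adverse event table by these classes would have overlapping groups.

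**Working it through.** **Inputs.** Rules as in Table 7; 16 weeks = 16 × 7 = 112 days. ADA sampling on Days 15, 30, 60, 90, 180 and 270 is an assumption, since the SAP lists those days for neutralizing antibodies. Counts are of possible result patterns with at least one positive, not of expected patients.

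**Overlap: post-baseline rows, and treatment-emergent rows for baseline-negative patients**

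*Last sample Day 270.* Transient needs Day 270 negative and either one positive or a span under 112 days. Any non-empty set from Days 15, 30, 60, 90 qualifies (longest span 75 days): 2⁴ − 1 = 15. Day 180 alone qualifies, and so does Days 90 and 180 (span 90); Days 60 and 180 does not (span 120). Total 17. The recency rule catches Day 180, because 270 − 180 = 90 < 112, so 2 of the 17 are also persistent. Persistent patterns: 32 with Day 270 positive, plus 16 with Day 270 negative and Day 180 positive = 48.

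*Last sample Day 180.* The 15 sets from Days 15 to 90 are transient. A Day 90 positive is 90 days before the last sample (caught); Day 60 is 120 days before (not caught). Sets containing Day 90: 2³ = 8. Persistent: 16 + 8 = 24.

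*Last sample Day 90.* The 2³ − 1 = 7 sets from Days 15, 30, 60 are transient, and every one has a positive within 75 days of the last sample, so all 7 are also persistent. Persistent: 8 + 7 = 15.

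| Last sample | Positive patterns | Transient | Persistent | Both | Transient + persistent |
|---|---|---|---|---|---|
| Day 270 | 63 | 17 | 48 | 2 | 65 |
| Day 180 | 31 | 15 | 24 | 8 | 39 |
| Day 90 | 15 | 7 | 15 | 7 | 22 |

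The table's identity would need 63, 31 and 15 in the last column.

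**Gap: treatment-emergent rows, baseline-positive patients**

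Take a titre of at least 4 times baseline at Day 30, twice baseline at Day 90, and negative at all other visits including Days 180 and 270. The Day 30 sample makes the patient treatment-emergent positive. Then:

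- transient 3a fails: there are two positives;
- transient 3b fails: the Day 90 titre is below 4 times baseline;
- persistent 2 fails: the span is 60 days, and the Day 90 titre is too low;
- persistent 3 fails: the last sample is negative;
- persistent 4 fails: the only titre of at least 4 times baseline is 270 − 30 = 240 days before the last sample.

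The patient is in neither class.

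With four levels per visit (negative, same as baseline, twice, at least 4 times) there are 4⁶ − 3⁶ = 4,096 − 729 = 3,367 treatment-emergent patterns. The number in neither class depends on three readings the SAP leaves open: whether a last sample the same as baseline (transient) means the identical titre or anything below 4 times, the same question for similar to baseline (persistent), and whether 3b counts a last sample that is still positive at baseline level. The eight combinations run from 1,530 to 1,812 patterns (1,530/3,367 = 45%; 1,812/3,367 = 54%).

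**The exactly-16-week case.** Spans of exactly 112 days satisfy neither span rule; positives at Days 30 and 142 with a negative Day 270 would be unclassified. On the listed days, however, the possible spans jump from 90 to 120 days, so this does not arise. In 200,000 random baseline-negative patterns with an assumed ±4-day jitter, none was unclassified.

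**The case against.** **Importance.** Immunogenicity is secondary in Phase 1b and exploratory in Phase 2. The outputs are descriptive, by-patient listings are provided, and the adverse event overview that will be repeated by ADA status uses post-baseline positive versus negative, which splits cleanly. This stands, and it limits the weight of the point.

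**Conditional outputs.** A reader might infer that a committed safety analysis by transient and persistent status is compromised. The SAP does not support that: the adverse event split is optional, and the treatment-emergent split, the only place the sum note applies, depends on the data. The post-baseline transient and persistent counts are committed, though, and they carry the overlap.

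**Scope of the 4-times rule.** It would be wrong to say that all the baseline-positive rules require every positive to reach 4 times baseline. Only transient 3b and persistent 2 do; persistent 3 looks at the last sample and persistent 4 at one earlier sample. A looser reading, in which only titres of at least 4 times baseline count as positives throughout and any lower last sample counts as back to baseline, would close the gap on the listed days. That is not what the text says, and it leaves the overlap untouched.

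**Pattern counts.** A reader might infer that about half of baseline-positive patients with treatment-emergent ADA would be lost. The count is unweighted, uses an arbitrary four-level grid, and moves with undefined terms. The number of baseline-positive patients is not given.

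**Schedule.** The ADA days, and whether early leavers give a final sample, are for the protocol. The figures for Days 180 and 90 apply only if the last sample falls there.

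**Conclusion.** The definitions are wrong as written and should be corrected before database lock. The overlap is the main defect: it arises on the listed days, affects committed counts, and grows as follow-up shortens (2 of 17, 8 of 15, then 7 of 7 transient patterns). It alone makes the sum note false. The baseline-positive gap is real but limited to the treatment-emergent rows in those patients; 1,530 to 1,812 of 3,367 patterns describes the rules and is not an estimate of patients affected. The exactly-16-week hole is theoretical on the listed days.

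These results assume that ADA is sampled on the neutralizing antibody days and that the rules are applied literally with no precedence. The consequence is confined to descriptive immunogenicity summaries and the optional adverse event breakdown. Nothing in the SAP text at hand links these classes to the primary SRI-4 analysis.

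**What to change.** Make the classes a partition:

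1. **Classify persistent first:** qualifying positives 16 weeks or more apart, or a qualifying positive at the last sample, or the last qualifying positive less than 16 weeks before the last sample.
2. **Define transient as the remainder:** every other post-baseline positive patient, or every other treatment-emergent positive patient in those rows.
3. **Define qualifying:** any confirmed positive in the post-baseline rows and for baseline-negative patients (missing baseline is already treated as negative). In the treatment-emergent rows for baseline-positive patients, count only titres at least 4 times baseline, at the last visit as well. The terms same as and similar to baseline are then no longer needed.

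Check on the full listed schedule. Baseline negative: 48 persistent + 15 transient = 63. Baseline positive: persistent is 4⁵ = 1,024 with a qualifying last sample, plus 3 × 4⁴ = 768 with a qualifying Day 180 sample and a non-qualifying last one, giving 1,792; transient is 3,367 − 1,792 = 1,575. Precedence alone would not be enough: it removes the overlap but leaves the baseline-positive gap.

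The cost is SAP wording and derivation code. The transient count falls by the overlap. The persistent count does not rise for baseline-negative patients on the listed days, since those double counted already appear there. Baseline-positive patients now in neither class join one or the other.
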